2.2 Secondary Objectives

1. To describe the adverse events associated with FOLFIRINOX when administered preoperatively in patients with resectable pancreatic cancer.
2. To estimate the fraction of patients who can successfully undergo surgery after neoadjuvant chemotherapy.
3. To estimate the overall resectability rate, rate of R0 resection, disease free survival (DFS), overall survival (OS), overall response rate (ORR; complete response (CR) + partial response (PR)), and disease control rate (DCR; CR + PR + stable disease (SD)) after administration of FOLFIRINOX in patients with resectable pancreatic cancer.

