8. TOXICITIES TO BE MONITORED/DOSAGE MODIFICATIONS

Adverse events will be recorded for all patients beginning at C1D1 (i.e. start of neoadjuvant treatment) through 30 days post completion of neoadjuvant therapy or progression.

Each patient will be assessed for the development of any toxicity according to the Study Calendar (Section 10). Toxicity will be assessed according to the NCI Common Terminology Criteria for Adverse Events (CTCAE), version 4. Dose adjustments should be made according to the system showing the greatest degree of toxicity.

The treating physician may use his/her best clinical judgment when determining dose adjustments and/or holds. Dose adjustments of each agent may be made independently of dose modifications of the other agents (Table 3), and are based on the specific types of toxicities observed (Table 4). Agents held more than 14 days for toxicity should be discontinued. If more

than 2 dose reductions of a single agent in a patient are required, that agent will be discontinued. Once a dose reduction has been performed, no intra-patient dose re-escalation is permitted. Patients that have treatment delays for more than 14 days during any of the 6 cycles of chemotherapy should be removed from the study.

Additional detailed information on the potential adverse events and risks associated with each agent is included in Section 13.

Dose Level	Irinotecan	5FU Bolus / Infusion	Oxaliplatin	Leucovorin*
Starting dose (level 1)	180 mg/m ²	400/2400 mg/m ²	85 mg/m ²	400 mg/m ²
-1	150 mg/m ²	320/2000 mg/m ²	65 mg/m ²	400 mg/m ²
-2	120 mg/m ²	240/1600 mg/m ²	50 mg/m ²	400 mg/m ²

**If 5FU is discontinued, leucovorin is simultaneously discontinued.*

On Day 1 or Day 15	Toxicity at any point during cycle	Dose Level for Subsequent Administration		
Hematologic Toxicities				
If ANC <1.5 on the day of treatment, treatment will be delayed ² for 1 week. Resume treatment when ANC ≥1.5.	Neutropenia	Irinotecan	5FU	Oxaliplatin
	Grade 2	Maintain dose	Maintain dose	Maintain dose
	Grade 3	↓1 dose level	↓1 dose level	↓1 dose level
	Grade 4	↓2 dose levels	↓2 dose levels	↓2 dose levels
	Febrile neutropenia	↓2 dose levels	↓2 dose levels	↓2 dose levels
If platelets <75K on the day of treatment, delay ¹ treatment for 1 week. Resume treatment when platelets ≥75K.	Thrombocytopenia²	Irinotecan	5FU	Oxaliplatin
	≤Grade 1	Maintain dose	Maintain dose	Maintain dose
	Grade 2-3	↓1 dose level	↓1 dose level	↓1 dose level
	Grade 4	↓2 dose levels	↓2 dose levels	↓2 dose levels

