9.2 Surgical Resection

Approximately 4 weeks (+/- 2 weeks) after the completion of the neoadjuvant treatment, patients will undergo standard of care operative exploration and complete extirpative surgery. Operative planning will be based on the original review of the patients' initial (i.e. pre-treatment) staging CT or MRI scan and the scan obtained after completion of the neoadjuvant protocol. All patients will undergo two modalities of operative exploration for occult metastatic disease undetectable with conventional cross-sectional imaging. Prior to laparotomy, patients will undergo a formal two-port staging laparoscopy to exclude the presence of occult metastatic disease involving the liver or peritoneal surfaces. Suspicious nodules possibly representing metastatic disease will be biopsied to confirm a pathologic diagnosis of metastatic pancreatic adenocarcinoma. Proof of metastatic cancer (i.e. stage IV cancer) will exclude patients from operative resection of the primary pancreatic cancer. In the absence of metastatic disease detectable with staging laparoscopy, patients will undergo a formal laparotomy with abdominal exploration to exclude occult metastatic disease involving the peritoneal surfaces or liver.

In the absence of occult metastatic disease, patients will undergo the planned operative procedure to resect the primary pancreatic adenocarcinoma completely. Based on preoperative imaging,

patients will undergo either a pancreatoduodenectomy (PD) or distal pancreatectomy and splenectomy (DPS). PD will be performed for patients with head and/or neck of pancreas cancers. DPS will be performed for patients with body and/or tail of pancreas cancers. PD and DPS will be performed according to standardized techniques which are employed routinely at Indiana University Hospital.

All margins of resection will be sampled intraoperatively to ensure complete clearance. For PD, the neck of pancreas and bile margins will be reviewed with frozen section histopathologic analysis. For DPS, the proximal pancreatic margin (i.e. body or neck of pancreas) will be reviewed intraoperatively. Final margin status (R0 versus R1) of the resected specimens will be recorded in addition to the intraoperative margin status assessments.

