All complications within 30 days of operative resection will be recorded prospectively and comprehensively according to the data acquisition guidelines of the American College of Surgeons National Surgical Quality Improvement Program (ACS-NSQIP). All patients undergoing pancreatectomy at Indiana University Hospital are included in the ACS-NSQIP database which has been modified to contain complications variables specific to pancreatic procedures.

Patients will receive a routine, formal clinical evaluation by their respective surgeon as per institutional guidelines and standard of care. Postoperative complications will be recorded during this evaluation and will be treated according to standardized practices. Patients will be evaluated for post-operative adjuvant chemotherapy within 4-6 weeks from the date of the operation as is routinely done after surgery. Further adjuvant treatment will be determined at the treating physician's discretion (i.e. chemoradiotherapy or adjuvant chemotherapy).

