14.3 Statistical analysis plan

Primary Outcome:

- Pathologic complete response: the proportion of the 48 patients having a pathologic complete response with a 95% confidence interval (using normal approximation) will be calculated.

Secondary Outcomes:

- *Safety:* Adverse events of grades 3, 4, 5 by the CTCAE v4.3 criteria for each category listed in section 2.1.6 will be summarized. The proportion of patients with each category of AE will be calculated with a 95% confidence interval. After the enrollment of the first 20 patients, we will evaluate the rate of surgical resection. If >6 patients are not able to proceed with surgery due to excessive toxicity or progression (not including occult metastatic peritoneal disease that was found during surgery and not on imaging) the study will discontinue due to unacceptable toxicity.

- *Ability of patients to undergo surgical resection after receiving neoadjuvant FOLFIRINOX*: the proportion of patients who are able to go through surgery among those who have resectable tumor will be calculated accompanied with a 95% confidence interval.
- *Rate of resectability* will be evaluated by determining the proportion of patients who are able to undergo surgery with resection of their primary tumor (R0 vs R1) resection. A 95% confidence interval will be constructed for the rate.
- *Disease free survival (DFS)*: DFS is defined as time from registration to evidence of tumor recurrence (including clinical deterioration related to the underlying pancreatic cancer, as assessed by the investigator) or death from any cause. Kaplan-Meier curve for DFS will be plotted. Median DFS time will be calculated accompanied with a 95% confidence interval.
- *Overall survival*: time from registration to death for 48 patients with right censoring will be analyzed using Kaplan-Meier estimate. Median survival time will be obtained accompanied with a 95% confidence interval.
- *Objective response rate*: proportion of patients with complete responses (CR) or partial responses (PR) after 4 cycles of FOLFIRINOX treatment will be constructed with a 95% confidence interval.
- *Disease control rate*: Proportion of patients with complete responses (CR), partial responses (PR), or stable disease (SD) after 4 cycles of FOLFIRINOX treatment will be obtained with a 95% confidence interval.

Tertiary Outcomes:

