18.1.4 Determining Attribution to the Investigational Agent(s)

Attribution: An assessment of the relationship between the AE and the medical intervention. CTCAE does not define an AE as necessarily “*caused by a therapeutic intervention*”. AEs will be monitored until they are resolved or are clearly determined to be due to a subject’s stable or chronic condition or intercurrent illness.

After naming and grading the event, the clinical investigator must assign an attribution; or the determination of whether an adverse event is related to a medical treatment or procedure. The categories of attribution are described below:

Relationship	Attribution	Description
Unrelated to investigational agent/intervention	Unrelated	The AE is clearly NOT related
	Unlikely	The AE is doubtfully related
Related to investigational agent/intervention	Possible	The AE may be related
	Probable	The AE is likely related
	Definite	The AE is clearly related

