18.2 Adverse Event (AE) Reporting

Adverse events (AEs) will be recorded from the time of first study drug administration and for at least 30 days after treatment discontinuation, regardless of whether or not the event(s) are considered related to trial medications. All AEs considered related to trial medication will be followed until resolution, return to baseline, or deemed clinically insignificant, even if this occurs post-trial.

18.2.1 Reporting to the Data Safety Monitoring Committee (DSMC):

Regardless of study sponsorship, the DSMC chair and/or coordinator will review all expedited SAE reports through OnCore®. Expedited reports are completed per IRB guidelines and may include the IRB Prompt Reporting form, and/or non-compliance form. Submission of this information to the DSMC is **additional to** any other protocol-specified regulatory bodies (e.g. FDA, pharmaceutical company) to be notified. When follow-up information is received, a follow-up report should also be created in OnCore®. The DSMC chair and/or coordinator will review expedited SAE reports monthly.

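### The grade 3–5 adverse event rates mix chemotherapy toxicity with a share of surgical morbidity that depends on the operation date, and Sections 8 and 18.2 define the recording window differently

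*Combined protocol and SAP*

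**What the plan says.** **Recording window.** Section 8 starts recording at the first dose and continues "through 30 days post completion of neoadjuvant therapy or progression". Section 18.2 also starts at the first dose but continues "for at least 30 days after treatment discontinuation, regardless of whether or not the event(s) are considered related to trial medications". It has no exception for progression and sets no upper limit.

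**Surgery.** Section 9.2: "Approximately 4 weeks (+/- 2 weeks) after the completion of the neoadjuvant treatment, patients will undergo standard of care operative exploration". The same section sets up a second record: "All complications within 30 days of operative resection will be recorded prospectively and comprehensively", following the national surgical quality programme's data guidelines.

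**Analysis.** The first secondary objective (Section 2.2) is: "To describe the adverse events associated with FOLFIRINOX when administered preoperatively in patients with resectable pancreatic cancer". Section 14.3 serves it with two sentences: "Adverse events of grades 3, 4, 5 by the CTCAE v4.3 criteria for each category listed in section 2.1.6 will be summarized", and "The proportion of patients with each category of AE will be calculated with a 95% confidence interval". Neither says how an event that begins after the operation is counted. Section 18.1.4 makes attribution compulsory ("After naming and grading the event, the clinical investigator must assign an attribution"), but Section 14.3 does not use it. Nor does Section 14.3 plan any summary of the postoperative complication record.

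**The concern.** The objective is to describe the toxicity of chemotherapy given before surgery. The recording window runs past the point at which many patients will have been operated on, and events are recorded whether or not they are thought related to treatment. Under these rules a severe complication of pancreatectomy on day 20 enters the same table as a severe chemotherapy toxicity. The same complication in a patient operated on at day 35 does not.

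Two patients with identical chemotherapy toxicity can therefore be counted differently because their operations were booked on different dates. The study rationale (Section 1.4) presents the safety findings as a foundation for later combinations, so readers will compare these rates with other regimens and need to know what the rates contain. Meanwhile the complete record of surgical morbidity after neoadjuvant treatment is collected but has no place in the analysis.

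Separately, two sections define the window in different words. Site staff and the analyst could follow either one.

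**Working it through.** The plan gives no figure of its own on this point, so there is none to reproduce. The check is date arithmetic, with day 0 as completion of neoadjuvant therapy.

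**Inputs**
- End of the 30-day window: day 30 (Section 8; Section 18.2 sets this as a minimum).
- Surgery: 4 weeks ± 2 weeks = 28 ± 14, so days 14 to 42 (Section 9.2).
- Postoperative record: 30 days from resection (Section 9.2).

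**Postoperative days inside the window** = max(0, 30 − day of surgery)

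| Day of surgery | Days captured | Share of the 30 postoperative days |
|---|---|---|
| 14 | 30 − 14 = 16 | 16/30 = 53% |
| 21 | 30 − 21 = 9 | 9/30 = 30% |
| 28 | 30 − 28 = 2 | 2/30 = 7% |
| 30 or later | 0 | 0% |

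If surgery were spread evenly over whole days 14 to 42 (an assumption; the plan centres it near day 28), the average would be (16 + 15 + … + 1)/29 = 136/29 = 4.7 days, or 15.6% of the postoperative period. Days 30 to 42, which are 13 of the 29 (45%), would contribute none.

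**Possible effect on a reported rate.** The documents give neither a chemotherapy nor a surgical grade 3–5 rate for this setting, so these are assumed values for illustration. Let C be the chemotherapy rate and M the 30-day surgical rate, with constant hazard and independence. With d postoperative days captured, the recorded rate is 1 − (1 − C)(1 − M)^(d/30).

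- C = 40%, M = 30%, surgery on day 14: 1 − 0.60 × 0.70^(16/30) = 50.4%.
- Same C and M, surgery on day 28: 1 − 0.60 × 0.70^(2/30) = 41.4%.
- Same C and M, surgery on day 42: 40.0%.
- C = 40%, M from 20% to 40%, surgery on day 14: 46.7% to 54.3%.
- C = 60%, M from 20% to 40%, surgery on day 14: 64.5% to 69.5%, against 60.0% for surgery on day 42.

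**The two window definitions side by side.** The mention of progression in Section 8 can be read in two ways. If recording stops at progression, a patient progressing on day 0, 14 or 28 after completion loses 30, 16 or 2 days of a 30-day window. If recording runs for 30 days after progression, such a patient loses none. Section 18.2 loses none on either reading. The sections also differ in their anchor (completion against discontinuation) and in the end point (a fixed 30 days against a minimum of 30).

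**The case against.** **The effect is small at the planned date.** Surgery is aimed at about 4 weeks, and at day 28 only 2 of 30 postoperative days fall inside the window. The 53% is the extreme edge, and the 15.6% average needs an even spread of dates that the plan does not state. This is fair. The mixing is still real for any patient operated on before day 30.

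**The data allow separation.** Attribution is recorded for every event and surgical complications have their own record, so nothing is lost. This also stands, and it makes the point one of unspecified tabulation. But Section 14.3 specifies no separation. It refers to a category list in a Section 2.1.6 that does not appear in the document, so one cannot tell whether surgical categories are in or out.

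**A reader might infer that recording is cut short in progressors.** The documents do not establish this. It follows from only one reading of Section 8. Section 18.2 sets a 30-day minimum with no exception, and the study calendar gives every patient, including those who discontinue, an adverse event assessment at the surgical evaluation visit. Nor can the number affected be estimated. The 14% progression figure in Section 1.3 is 3 of 21 patients with borderline resectable or locally advanced disease, whereas this trial enrols resectable disease only.

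**A reader might also infer that the days between day 30 and a late operation go unrecorded.** That is not shown either. Section 18.2 says at least 30 days, the calendar assessment can fall as late as day 42, and events considered related are followed to resolution, return to baseline or clinical insignificance.

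**Conclusion.** The concern holds in two parts. First, Sections 8 and 18.2 give different recording windows, and the reference to progression in Section 8 is ambiguous; the two must be reconciled. Second, with a 30-day window and Section 14.3 followed as written, the preoperative FOLFIRINOX rates include from 0 to 16 postoperative days per operated patient, depending only on the date of surgery, and the 30-day complication record has no planned summary.

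The 0 to 16 range rests only on the stated timings. The effect on a reported percentage depends on event rates that the documents do not give: about 5 to 14 percentage points for surgery on day 14 under the values assumed above, and close to nil for surgery near day 28 or later.

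This affects a secondary, descriptive objective. It does not touch the primary endpoint. The stopping rule is also unaffected, because it counts patients who fail to reach surgery and does not use these proportions. The change is still worth making, because it is almost free and the data are already being collected.

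**What to change.** 1. **Sections 8 and 18.2:** state one adverse event window, with one anchor and one end point, for all patients. Say explicitly what progression does to it.

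2. **Section 14.3, adverse events:** report grade 3–5 CTCAE events within that window, split by onset before surgery versus on or after surgery. For the second group, show the recorded attribution so that chemotherapy-related events with onset after an operation are kept. Keep the combined figure as well, because time before surgery still differs between patients. Simply ending the count on the day before surgery would be worse: follow-up after treatment would run from 13 to 41 days (14 − 1 to 42 − 1), and chemotherapy-attributed events after an early operation would be dropped.

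3. **Section 14.3, postoperative outcomes:** add a separate summary of 30-day complications and deaths among resected patients from the Section 9.2 record, with exact 95% confidence intervals. Report patients explored but not resected separately, because that record is tied to resection and may not cover them.

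**Cost:** a wording change and one extra table. The split uses event dates, operation dates and attributions, and the new summary uses the record already kept under Section 9.2.

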9. STUDY PROCEDURES

9.1 EUS or CT-Guided Biopsy Procedure

Pancreatic cancer is commonly staged by the means of endoscopic ultrasound (EUS). This is a standard of care procedure which includes minimal sedation and upper endoscopy. A linear echoendoscope will be utilized to identify the pancreatic mass. A fine needle aspirate (FNA) or core biopsy will be performed at the same time. As with standard practice, biopsy will be performed with on-site cytology review to confirm malignancy. All diagnostic biopsies must be reviewed by the Pathology Department per the institutional guidelines.

If patients do not proceed to surgery after neoadjuvant treatment (may occur if the patient refuses surgery, is not eligible for surgery or has progression of disease), then an optional biopsy may be completed at the end of treatment. In these cases, a CT-guided biopsy will likely be performed. EUS biopsies are typically performed for patients who have localized disease while CT-guided biopsy is typically performed when metastatic disease is suspected.

Biopsies may be performed prior to patient enrollment as they are standard of care for pancreatic cancer diagnosis. Therefore, tissue samples being stored with the Pathology Department (i.e. archival tissue) in lieu of fresh tissue collection may be requested after enrollment to satisfy the baseline tissue collection requirement of this study. Additionally, it may be difficult to coordinate fresh tissue collect at the time of surgical resection (see below) or biopsy; therefore, archival tissue may also be collected to satisfy the post-neoadjuvant treatment tissue collection requirement of this study.

Additional details regarding tissue collection can be found in Section 12.1.

9.2 Surgical Resection

Approximately 4 weeks (+/- 2 weeks) after the completion of the neoadjuvant treatment, patients will undergo standard of care operative exploration and complete extirpative surgery. Operative planning will be based on the original review of the patients' initial (i.e. pre-treatment) staging CT or MRI scan and the scan obtained after completion of the neoadjuvant protocol. All patients will undergo two modalities of operative exploration for occult metastatic disease undetectable with conventional cross-sectional imaging. Prior to laparotomy, patients will undergo a formal two-port staging laparoscopy to exclude the presence of occult metastatic disease involving the liver or peritoneal surfaces. Suspicious nodules possibly representing metastatic disease will be biopsied to confirm a pathologic diagnosis of metastatic pancreatic adenocarcinoma. Proof of metastatic cancer (i.e. stage IV cancer) will exclude patients from operative resection of the primary pancreatic cancer. In the absence of metastatic disease detectable with staging laparoscopy, patients will undergo a formal laparotomy with abdominal exploration to exclude occult metastatic disease involving the peritoneal surfaces or liver.

In the absence of occult metastatic disease, patients will undergo the planned operative procedure to resect the primary pancreatic adenocarcinoma completely. Based on preoperative imaging,

patients will undergo either a pancreatoduodenectomy (PD) or distal pancreatectomy and splenectomy (DPS). PD will be performed for patients with head and/or neck of pancreas cancers. DPS will be performed for patients with body and/or tail of pancreas cancers. PD and DPS will be performed according to standardized techniques which are employed routinely at Indiana University Hospital.

All margins of resection will be sampled intraoperatively to ensure complete clearance. For PD, the neck of pancreas and bile margins will be reviewed with frozen section histopathologic analysis. For DPS, the proximal pancreatic margin (i.e. body or neck of pancreas) will be reviewed intraoperatively. Final margin status (R0 versus R1) of the resected specimens will be recorded in addition to the intraoperative margin status assessments.

All complications within 30 days of operative resection will be recorded prospectively and comprehensively according to the data acquisition guidelines of the American College of Surgeons National Surgical Quality Improvement Program (ACS-NSQIP). All patients undergoing pancreatectomy at Indiana University Hospital are included in the ACS-NSQIP database which has been modified to contain complications variables specific to pancreatic procedures.

Patients will receive a routine, formal clinical evaluation by their respective surgeon as per institutional guidelines and standard of care. Postoperative complications will be recorded during this evaluation and will be treated according to standardized practices. Patients will be evaluated for post-operative adjuvant chemotherapy within 4-6 weeks from the date of the operation as is routinely done after surgery. Further adjuvant treatment will be determined at the treating physician's discretion (i.e. chemoradiotherapy or adjuvant chemotherapy).

